despite their positive screening results. The entire 4,000 subjects will be followed for 12 months. Across the various primary care practices, we will have access to more than 12,000 adults aged 65 and older. From our prior screening studies, we know that the prevalence of screening positive for possible dementia is 13-15% and of these, 50% will have dementia on subsequent diagnostic assessments. Although we have designed this study as a pragmatic trial, we will be requesting that patients sign informed consent for participation in the project.

Telephone Recruitment:

We will also employ a telephone version of the informed consent process to allow for potential recruitment of previously identified eligible patients via the INPC that were not approached in clinic by the ResNet team due to time and prioritization restraints. We will obtain a list of the eligible participants that were not approached from the PBRN Program Manager on a regular basis. These participants will be contacted for participation by telephone by study research assistants. We will also utilize the same telephone consenting process to recruit subjects attending the IU Health Arnett primary care clinics. Eligible patients from the IU Health Arnett primary care clinics will be identified by the treating physician and a list generated for the study research team.

Screening Process

Both subjects who are randomized into the non-screening arm of the study and those who are randomized into the screening arm will complete a set of standardized questions about successful aging, preventive health measures, and lifestyle behaviors. This is to invest the patients randomized into the non-screening arm of the study in the project, minimize the potential excess focus on cognitive screening alone, and to remove any impressions among the “non-screened” group that they missed out on an important health screen. We have not pre-specified the content of this screener because it will be designed based on ongoing data collection in the two targeted health care systems. This is consistent with our approach to embed the project, whenever possible, into ongoing or emergent activities. Examples of

questions to include in this control questionnaire might include: smoking, physical activity, influenza vaccination, or seat belt use for example. At the time of this questionnaire, enrolled subjects will also complete the baseline study assessment described later in this proposal.

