Prescription records for all patients enrolled in the study will be reviewed using the Indiana Network for Patient Care to evaluate the use of psychotropic medications such as anticholinergics, antidepressants, anxiolytics and antipsychotics. These psychotropic medications will be categorized based on the American Hospital Formulary Service system criteria into anti-dementia (including cholinesterase inhibitors or memantine), antipsychotics, antidepressants, and anxiolytics.¹²¹

Care Processes

We will use the web-based tracking system (eMR-ABC) and INPC to monitor multiple processes of dementia care measures for both the control and the intervention groups including all patient contacts by the local memory care or primary care practices, the referral to local Alzheimer disease support groups, the use of home health services, and assessment of the level of participation of patients and caregivers in the collaborative care intervention program.

Advanced Care Planning (ACP)

We will measure the subjects' advanced care planning including having power attorney for health care and/or financial affairs, having a living will, and having life and additional insurance policies at baseline and 12 months. Advocates for dementia screening, even in the absence of highly effective anti-dementia drugs, argue that screening would offer patients a window of opportunity to complete ACP while most still have the capacity to do so. We are unaware of any data documenting that participation in a screening program for dementia or any other serious illness is associated with greater participation in ACP.

Dementia Recognition

We will determine the recognition of dementia by searching the Indiana Network for Patient Care databases for any ICD-9 code indicative of dementia or Alzheimer disease at hospital admission, discharge, or during the 12-month period following enrollment into the study.

I. Statistical Plan

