Secondary Aim 1 compares depression and anxiety levels at 1 month post dementia screening between screened subjects and subjects in the no screening group. ANCOVA models will be used to compare PHQ-9 and GAD-7 obtained at 1 month between the screening and no screening groups adjusting for patients’ characteristics and baseline measures.

Secondary Aim 2 estimates the cost effectiveness of the dementia screening program in comparison to the “no screening”. This economic evaluation will be conducted from the societal and payer perspectives, including the direct medical care costs, caregiver and patient time and transportation costs, and the effect on quality of life for patients and caregivers.¹²³ Costs will be

divided into fixed and variable costs and by the screening, initial assessment phase and the follow-up phase of treatment. Total medical care utilization costs will be estimated for the control and screening groups from healthcare utilization and reimbursement data captured by the Indiana Network for Patient Care (INPC) during the trial. Prescription drug use will also be obtained from the INPC healthcare administrative database. The cost analysis will capture the extent to which screening, early diagnosis and coordinated care of patients with Alzheimer's disease affects medical care costs associated with dementia and co-morbid conditions such as diabetes, made worse by failure to manage dementia. Activity costing will be utilized to estimate the costs necessary to implement and operate the screening and collaborative dementia care management program and the usual care for dementia patients. Patient and caregiver time, staff time, fringe benefits, overhead costs, and materials will be logged by staff using the eMR-ABC software and assessed for the 12 month follow-up period. Included are waiting time, time with patients, time in meetings, lab services, telephone calls and mailings to participants. Excluded are costs associated with research. Transportation costs will be estimated from data on distance from home to clinic. Health care contacts will be dated and checked to avoid double counting via claims and activity costing methods.

Prescription drugs will be valued at the median wholesale price. A dispensing fee will be added for each 100 doses. Unit wage costs and fringe benefits will be standardized applying median values paid to personnel in the region; wage data collected from the health care system partners.

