Costs will be accumulated during the trial based on the probability of survival each month times the monthly cost of care for survivors to address censoring.¹²⁴ Effects and costs will be discounted at a 3% annual rate for the two-year trial period. The incremental CE ratio (ICER), will compare the no screening and less resource intensive usual care treatment strategy (UC) with the screening coupled with the more intensive treatment intervention (the

collaborative dementia care program) using the following formulas for (1) dementia patients (AP) and (2) Dementia patients plus their caregivers (CG).

$$ICER_{AP} = [COST_{HABC} - COST_{UC}] \div [QALY_{HABC} - QALY_{UC}] \quad (1)$$

$$ICER_{AP+CG} = [COST_{HABC} - COST_{UC}] \div [QALY_{HABC} - QALY_{UC}] \quad (2)$$

Uncertainty in the cost-effectiveness ratios and 95 percent confidence intervals will be assessed with 1,000 bootstrap samples. The outcome of each sample will be expressed as a scatter plot of incremental costs and effects generated from the bootstrap samples, reflecting the uncertainty arising from the model parameters. Results will also be displayed using net benefit analysis and cost-effectiveness acceptability curves (CEAC).¹²⁵ There is controversy about the appropriate ceiling ratio for health benefits.¹²⁶ Garber et al have recommended that a value of twice the median annual per capita income will result in efficient resource allocation.¹²⁶ The effects on ICERs of alternative unit cost estimates for care-giver time value and overhead cost rate for the screening and coordinated care management will be examined in a series of one-way and multi-way sensitivity analyses. The ceiling ratio λ will be varied from \$30,000 to \$150,000 per QALY for the CEAC analysis. The cost-effectiveness hypothesis will be tested against the \$100,000 per QALY maximum willingness to pay norm.

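### The planned patient-plus-caregiver ICER has no caregiver utility behind it and, as printed, repeats the patient ratio; one ICER on all randomised subjects should replace both

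*Combined protocol and SAP*

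**What the plan says.** Section I, Secondary Aim 2, sets out an economic evaluation from a societal and a payer viewpoint. Its scope includes "the effect on quality of life for patients and caregivers". It then gives two ICERs, "using the following formulas for (1) dementia patients (AP) and (2) Dementia patients plus their caregivers (CG". They are printed as "ICER_{AP} = [COST_{HABC} - COST_{UC}] \div [QALY_{HABC} - QALY_{UC" and "ICER_{AP+CG} = [COST_{HABC} - COST_{UC}] \div [QALY_{HABC} - QALY_{UC" (closing brackets left off here).

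On resource use, the same section says: "Patient and caregiver time, staff time, fringe benefits, overhead costs, and materials will be logged by staff using the eMR-ABC software". Section H (Care Processes) adds that eMR-ABC and the regional record exchange (INPC) will track dementia care processes "for both the control and the intervention groups".

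On the horizon, section I says: "Effects and costs will be discounted at a 3% annual rate for the two-year trial period". Section E (Subject Recruitment) says: "The entire 4,000 subjects will be followed for 12 months".

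The hypothesis in the aims statement is that screened subjects will have an ICER below $100,000 per QALY at 12 months. It does not mention caregivers.

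**The concern.** A ratio for patients plus caregivers needs caregiver QALYs in both arms. If none are collected, the analyst can only reprint the patient ratio under a second label or fill the gap with caregiver utilities assumed after the fact. Cost effectiveness is a named aim with a fixed threshold, and the results are meant to inform policy-makers, so neither outcome is acceptable.

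The population is a second problem. The ratios are written for dementia patients, but the trial randomises undiagnosed older adults and looks for dementia systematically only in the screening arm. A ratio restricted to dementia patients would not compare groups formed by randomisation.

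Two smaller points sit in the same section. The plan does not say how patient and caregiver time is captured for controls seen outside the care program. The discounting period also disagrees with the length of follow-up.

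**Working it through.** The documents state no ICER, QALY difference or economic sample size, so there is no planned figure to reproduce. The check compares the texts and adds some arithmetic.

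**1. The two formulas.** Both right-hand sides are (COST_HABC - COST_UC) / (QALY_HABC - QALY_UC). Neither has a caregiver term, so as printed (2)/(1) = 1 for any data.

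**2. Where a utility could come from.**
- Section H: the HUI measures the enrolled subject's quality of life at baseline, 1, 6 and 12 months. PHQ-9, GAD-7 and the MOS social support items also come from the subject.
- Section E, data-source table: the survey rows list HUI, PHQ-9, GAD-7, MOS, demographics and advance care planning. There is no caregiver row.
- Section L, consent: covers the subject's own HUI, PHQ-9, GAD-7, MOS and record extraction.
- Section E, care program: caregivers complete the HABC Monitor, which covers patient symptoms and caregiver stress. It is used inside the program and is not described as a utility.

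No caregiver utility appears for either arm.

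**3. What a caregiver term could do.** Let k = caregiver QALY gain / patient QALY gain, and hold incremental cost fixed (an assumption). Then ICER(2)/ICER(1) = 1/(1+k).

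| k (assumed) | ICER(2)/ICER(1) |
|---|---|
| 0 | 1.00 |
| 0.5 | 0.67 |
| 1 | 0.50 |
| -0.5 | 2.00 |

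The documents give no value for k, so this shows only how far the answer depends on an input that is not collected.

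**4. Who counts as a dementia patient.** In the screening arm, section E expects 300 positive screens: 100 refuse assessment, 100 are found not to have dementia and 100 are diagnosed. The 2,000 controls get usual care and are not assessed. With the prevalences used elsewhere in the protocol, controls with dementia would number 2,000 × 0.06 = 120 (section L) to 2,000 × 0.15 = 300 (section I). Section H finds them only if usual care records a dementia code, and section B says at least half of dementia cases in a typical practice are undiagnosed. A dementia-only ratio would set about 100 screen-detected patients who accepted assessment against an unknown, differently selected subset of controls. The aims statement makes no such restriction.

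**5. Time costs.** Section I applies activity costing to screening, the care program and usual care, and then names eMR-ABC as the log. Section E lists eMR-ABC as a support tool of the care program. Section H extends eMR-ABC and INPC monitoring to controls, but the items listed are contacts, referrals, home health use and program participation, not time. The source of time data for controls outside the program is therefore unstated.

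**6. Discounting.** With a factor of 1.03^(-t) at month midpoints, the mean is 0.985 over months 1 to 12 and 0.971 over months 1 to 24. A factor common to costs and QALYs cancels in the ratio. At the extremes within 12 months, with all cost in month 1 and all QALYs in month 12, the discounted ratio is 1.0275 times the undiscounted one. With the timing reversed it is 0.9733 times. The effect is at most about 2.7%.

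**The case against.** The strongest reply is that the formulas are generic. The labels on the left and the sentence before them define the two populations, and the right-hand side is to be evaluated in each. That is a fair reading of the notation, and it means the identical right-hand sides alone prove little. It does not help with the data: under any reading the second ratio needs caregiver QALYs, and none are planned. Part of the HABC Monitor description was not available for this review, but the data-source table and the consent scope are, and neither names a caregiver utility.

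It is also fair to say that the hypothesis tested against $100,000 concerns screened subjects, so the missing caregiver data do not undermine that test. This stands. The HUI, PHQ-9 and GAD-7 analyses are likewise untouched.

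Three stronger readings are tempting and not supported.
- A reader might infer that time costs will be counted in the screening arm only. The plan includes usual care in its activity costing and extends eMR-ABC and INPC monitoring to controls. The gap is an unstated method, not a demonstrated one-sided count. If control time did go unrecorded, incremental cost would be biased upward, against screening, by an amount the documents do not allow us to estimate.
- A reader might price the time logged for program patients and call the result bias. That time is a genuine cost of the strategy under test, and its hours, wage and QALY gain would all have to be assumed.
- A reader might take the two-year discounting statement as a further reason the ratio cannot be computed. It is a text conflict with a small effect.

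**Conclusion.** The concern holds in this form: a separate caregiver-inclusive ICER cannot be estimated from the planned data, because no caregiver utility is collected in either arm and the second formula as printed equals the first. The ratios are also tied to dementia patients, a group that cannot be identified systematically among unscreened controls, while the hypothesis is about screened subjects.

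The numerical size is unknown. The factor 1/(1+k) assumes fixed incremental cost, and the values of k are illustrative. The control-time gap is one of specification. The discount conflict moves the ratio by at most about 2.7% within a 12-month horizon and by nothing when costs and effects share the same timing.

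This should be corrected, but it affects a secondary aim only. The conclusion rests on the data-source table, outcome section and consent scope being complete as to caregiver measures.

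**What to change.** Rewrite the cost-effectiveness part of section I as follows.

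- Delete the second formula and the stated effect on caregiver quality of life. Adding a caregiver utility in both arms is the alternative, but caregivers of unrecognised control patients could not be found systematically.
- Define one ICER comparing all subjects as randomised, with HUI-based QALYs over 12 months, and test it against $100,000 per QALY.
- Value patient and caregiver time for usual-care contacts in both arms from one source: INPC contacts multiplied by a standard time per contact. Keep the patient, caregiver and staff time logged in eMR-ABC for screening and the care program as intervention cost, so that home visits and telephone contacts are not lost. Check that no contact is counted under both headings.
- Reconcile the two-year discounting period with the 12-month follow-up.

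The cost is a rewrite of one section, with no new data collection. The downside is that no caregiver-inclusive ratio is reported. From the societal viewpoint, caregiver time would count as a cost while any caregiver health gain would not, and the report should state this as a limitation.

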Primary Specific Aim 2: Test the impact of dementia screening on the mood and anxiety symptoms of patient at baseline and 1, 6, and 12 months (i.e., primary potential harms).

(We hypothesize that screened subjects will not have higher depression or anxiety at one month post-screening (as measured by the Patient Health Questionnaire (PHQ-9) and Generalized Anxiety Disorder (GAD-7) scales)

Secondary Aims: Estimate the cost effectiveness of dementia screening.

(We hypothesize that screened subjects will have an Incremental Cost Effectiveness Ratio (ICER) below the maximum acceptable threshold of \$100,000 per quality adjusted life year saved at 12 months.)

B. Innovation

Pragmatic

Previous studies by our team and others have demonstrated that routine feedback of dementia screening scores, continuing medical education for dementia, and other passive educational interventions can improve rates of diagnosis, but not patient outcomes.^{12,28-32} We have shown that patients and families perceive potential harms from screening and that dementia screening can result in important incremental health care costs.^{21-23,33} Conversely, we and others have also already demonstrated that collaborative care, focused on non-

pharmacologic approaches to behavioral disturbances, can improve patient outcomes under experimental conditions.^{34,35} The innovation of this trial is in moving the process upstream to asymptomatic, older adults, cared for in typical but prepared community-based practices, to document actual benefits and harms, including costs. “Asymptomatic”, in the case of cognitive impairment, is paradoxical in some respects, but we denote asymptomatic to mean that the cognitive impairment is not a presenting symptom of the patient (just as hypertension is asymptomatic but can be detected by screening, cognitive impairment can be detected through screening tests).

Academic Community Partnership

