Statistical Power, derived from sample size estimate, is used to test the primary hypothesis that subjects in the screening group will have higher health related quality of life than the no screening group. Previous randomized trials comparing collaborative care to usual care in demented patients have stated effect size of 0.4 being clinically significant.^{34,35} Considering that the majority of patients in the screening group or the no screening group are not demented, the observable effect size between these two groups will be a combined effect size measure in the non-demented subjects and in those demented subjects receiving the collaborative dementia care program.

Assuming 85% sensitivity of screening instrument and 15% prevalence of dementia in this patient population, to achieve 80% power to detect a significance effect size of 0.094 between the screening group and the no screening group at $\alpha=0.05$ level (two-sided), and allowing 10% of patients with missing follow-up outcomes at 12 months, we need to enroll at least 3951 patients into the study. The effect size of 0.094 between the screening group and the no screening group reflects a difference of 0.40 SD between demented patients in the collaborative dementia care program and demented patients who were not screened and a difference of 0.06 SD in the majority of patients who are not demented in either group. We demonstrate in the table below that our planned sample size of 4,000 will have sufficient power to detect significant differences between the “screen” group and the “no screen” group under various scenarios assuming varying degrees of efficacy measures for the collaborative dementia care program and for the screening only subjects.

Estimated power with a total sample size of 4,000 comparing primary outcome measures between the screening group and the no screening group (two-sided at $\alpha=0.05$) allowing 10% of patients with missing outcomes at 12 months.			
Effect size of collaborative care in demented subjects	Effect size In non-demented subjects	Observable Effect Size	Power Estimate
0.3	0.07	0.091	77.9
	0.08	0.100	85.1
0.4	0.07	0.102	86.4
	0.08	0.110	91.0

For the Secondary Aims, given the sample size of 4000, we will have greater than 95% power to test the equivalence levels in PHQ-9 and GAD-7 at 1 month assuming equivalence differences of 0.6 (SD=5.1) on PHQ-9 and 0.5 (SD=3.2) on GAD-7 based on our previous studies in primary care patients.^{34,51,93,114-118}

J. Limitations

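### The cost-effectiveness hypothesis is defined on the ICER alone, with no condition on the sign of the QALY difference, so as written it is also met when screening costs more and lowers quality of life; net benefit should be the decision quantity

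*Combined protocol and SAP*

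**What the plan says.** The Secondary Aims paragraph, just before section B (Innovation), gives the hypothesis: "screened subjects will have an Incremental Cost Effectiveness Ratio (ICER) below the maximum acceptable threshold of" $100,000 per QALY saved at 12 months.

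Section I (Statistical Plan, Secondary Aim 2) returns to it: "The cost-effectiveness hypothesis will be tested against the" $100,000 per QALY norm. The same paragraph covers uncertainty ("Uncertainty in the cost-effectiveness ratios and 95 percent confidence intervals will be assessed with 1,000 bootstrap samples"), a plot ("The outcome of each sample will be expressed as a scatter plot of incremental costs and effects generated from the bootstrap samples") and two further outputs ("Results will also be displayed using net benefit analysis and cost-effectiveness acceptability curves (CEAC"). The ceiling ratio for the CEAC runs from $30,000 to $150,000, which includes the test value.

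Neither place requires a positive QALY difference, defines dominance, says how a negative ratio is to be read, or says which statistic makes the test.

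**The concern.** A ratio of cost difference to QALY difference orders options sensibly only while the QALY difference is positive. Once that difference can be negative, a negative ratio may mean cheaper and better or dearer and worse, and a small positive ratio may mean giving up health for little saving. A hypothesis that the ratio is below $100,000 does not separate these cases.

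A QALY loss is a live possibility here. The trial's stated objective is to weigh benefits against harms of screening, depression and anxiety are named as potential harms, and the section on risks says that the effect of a diagnosis on quality of life is unknown. The planned benefit is also small (0.094 SD), so a difference near or below zero would be no surprise. At stake is whether a named, thresholded hypothesis meant to inform policy-makers could be reported as confirmed when screening is dominated.

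**Working it through.** **Inputs from the documents.** Threshold $100,000 per QALY (Secondary Aims; section I). Planned effect 0.094 SD, two-sided alpha 0.05, 80% power, 10% missing (section I, power). 4,000 subjects randomized 1:1 (section E). HUI SD 0.23, from primary care patients with dementia (section H), used as a stand-in for the QALY SD.

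**Assumptions, because the documents give no figures.** Extra cost $500 per screened subject; cost SD $5,000 to $15,000; costs and QALYs independent.

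**The plan's own figure.** No sample size or power is stated for cost-effectiveness. For the primary comparison, "to achieve 80% power to detect a significance effect size of 0.094 between the screening group and the no screening group" gives n per arm = 2 x (1.96 + 0.842)^2 / 0.094^2 = 1,777, or 3,554 in total. Then 3,554 / 0.9 = 3,949, against 3,951 stated, so the figure is reproduced within rounding. Evaluable per arm with 4,000 enrolled: 2,000 x 0.9 = 1,800.

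**Step 1: sign check, no distributional assumptions.** ICER = dCost / dQALY. Net monetary benefit (NMB) = 100,000 x dQALY - dCost.

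| dCost | dQALY | ICER | ICER below $100,000? | NMB |
|---|---|---|---|---|
| +$1,000 | +0.02 | +$50,000 | yes | +$1,000 |
| +$1,000 | -0.01 | -$100,000 | yes | -$2,000 |
| +$500 | -0.02 | -$25,000 | yes | -$2,500 |
| -$500 | -0.02 | +$25,000 | yes | -$1,500 |
| -$1,000 | -0.005 | +$200,000 | no | +$500 |

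The first row is read correctly. The next three meet the hypothesis with a negative net benefit. The last fails it although screening is good value at the threshold. Errors run in both directions whenever dQALY is negative.

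**Step 2: would a percentile interval of the ratio help?** Simulated trials, 1,000 bootstrap-type draws each, normal approximation. SE of dQALY = 0.23 x sqrt(2/1,800) = 0.0077. SE of dCost = $167 to $500.

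The larger loss is the planned effect with its sign reversed: 0.094 x 0.23 = 0.0216. The smaller is half of it, 0.0108. The smaller value is also the full-year QALY loss if a 12-month HUI difference of 0.0216 built up linearly from a balanced baseline.

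| True dQALY (dCost +$500) | Point ICER below $100,000 | Upper 97.5th percentile of ICER below $100,000 | Lower 2.5th percentile of NMB above 0 |
|---|---|---|---|
| -0.0216 | over 99% | about 78 to 84% | 0% |
| -0.0108 | about 94% | about 25 to 34% | 0% |

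The pass rate rises with the harm, because a clear QALY loss makes nearly every bootstrap ratio negative.

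**Step 3: what does net benefit cost when screening is good value?** With dCost +$1,000, dQALY +0.02, QALY SD 0.23 and cost SD $5,000 to $20,000, the net-benefit limit passes in 16 to 26% of trials and the ratio limit in 16 to 27%. Almost nothing is lost.

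**The case against.** The strongest reply is that the plan never adopts a wrong rule; it leaves the test statistic open. This is right as far as it goes. A reader might infer that the bootstrap interval of the ICER decides the hypothesis, but the sentence on bootstrapping says only how uncertainty is assessed. No text says that an interval limit must lie below $100,000, or that the interval is a percentile interval of the ratio. The results in Step 2 for that interval are therefore conditional. A net-benefit test at $100,000 would also be consistent with the sentence on testing. What remains is that the hypothesis itself is worded on the ratio, and no other statistic is attached to it.

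It can also be said that the hypothesis speaks of life years saved and the plan of willingness to pay, which presuppose a gain. That shows intent, but it is not a stated condition and gives no instruction for a negative difference.

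A reader might go further and infer that a harmful result would pass unnoticed. The documents do not support this. The scatter plot, net benefit analysis and CEAC are planned in the same paragraph and would show a dominated result. The two-sided primary HUI comparison would detect a loss of 0.094 SD with about 80% power. Nor does the plan say that the CEAC will be the share of ratios below the ceiling. These safeguards stand. Their limit is that they are introduced as displays, so an analyst could follow the plan, report the hypothesis as met, and print figures that contradict it.

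The simulated rates also depend on whole arms of 1,800, while the ICER formulas in section I are labelled for dementia patients, of whom about 100 screened subjects are expected to be diagnosed. With 100 per arm and a cost SD of $15,000, the ratio-interval pass rate is about 6% at a loss of 0.0216 and 70% at a loss of 0.092 (0.40 x 0.23). The rates do not carry over to that population.

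**Conclusion.** The concern holds for the hypothesis as worded. It is met by any negative ratio, including when screening costs more and lowers QALYs, and it can fail when screening is good value. That follows from the sign of the ratio and needs no assumption. Under the assumptions listed, the point ICER would meet the hypothesis in over 93% of trials at either true loss examined. A percentile interval of the ratio, if used, would do so in about 78 to 84% and 25 to 34%, and a net-benefit limit in 0%. These rates rest on assumed costs, a QALY SD borrowed from a dementia sample, and whole-arm comparisons.

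This is a gap in how a secondary hypothesis is defined, and it should be fixed. It does not affect the primary HUI analysis, and the documents do not support saying that the plan has fixed on a faulty test or would conceal harm.

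**What to change.** In the Secondary Aims and in section I, state the hypothesis as incremental net monetary benefit at $100,000 per QALY, 100,000 x dQALY - dCost, being greater than 0. Judge it by the bootstrap 95% interval of that quantity from the same 1,000 samples: the hypothesis is supported if the lower limit is above 0. Report the ICER as a descriptive figure, and where the QALY difference is not positive, state the quadrant (including dominant or dominated, where that applies) beside it. Keep the scatter plot and CEAC as planned.

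The cost is a few sentences of wording. No new data, samples or calculations are needed, since net benefit analysis is already planned, and Step 3 shows almost no loss of power.
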